6.8 Discontinuation or Withdrawal

6.8.1 Individual Subjects

If at any time during the study the investigator determines that it is not in the best interest of the subject to continue treatment, the subject's treatment will be discontinued. The investigator can discontinue the treatment for a subject at any time if medically necessary. If a subject's treatment is permanently discontinued by the investigator because of an AE, that AE should be indicated as the reason for treatment discontinuation. In this case, the subject is discontinued from the treatment, but still participates in the study and the subject is encouraged to follow the visit schedule and complete all assessments, particularly those at Week 12 and 24.

6.8.2 Treatment Modifications, Interruptions, and Discontinuation

If a subject experiences an LSR (AE) for the first time, the investigator must confirm if treatment is needed, if a treatment modification (hold treatment for certain areas) is needed, and/or if a treatment interruption (discontinue treatment in all areas) is needed. If the investigator confirms treatment is needed, the subject can continue study treatment on all areas, hold treatment in certain areas, or interrupt treatment completely, and add non-medicated treatment such as petroleum gel as a concomitant medication. This option can be exercised at any point during the study as needed.

If no concomitant treatment is added, the investigator may choose to withhold study treatment on either specific areas (modification) or all areas (interruption) until the investigator confirms it is appropriate to continue. It is recommended to modify or interrupt treatment for 2-3 days before re-starting the study treatment; the investigator should use their discretion for when to reinstate treatment by discussing the status of the AE with the subject/caregiver to determine if the event is resolved or if continued modification/interruption of study treatment is necessary. The investigator will confirm when reintroduction of study treatment can occur. This option can be exercised at any point during the study as needed.

For more severe AEs, concomitant treatment such as corticosteroids can be added while withholding study treatment on specific areas (modification) or all areas (interruption) until the investigator confirms it is appropriate to continue with the study drug. Similar to the modifications and interruptions above, it is recommended to modify or interrupt treatment for 2-3 days before re-starting the study treatment; the investigator should discuss the status of the AE with the subject/caregiver to determine if the event is resolved or if continued modification/interruption of study treatment is necessary. The investigator will confirm when reintroduction of study treatment can occur. This option can also be exercised at any point during the study as needed.

After the resolution of the first LSR and reinitiation of treatment, if a more severe second LSR occurs, it is appropriate to suspect the cause is allergic contact dermatitis. Study treatment on all areas should be discontinued, and after resolution of the second LSR, patch testing is

recommended if the subject/caregiver consents. This step should be exercised only if the LSR is more severe than previous LSR(s). See [Appendix 1](#) for additional information.

6.8.2.1 Temporary Treatment Discontinuation

The investigator may instruct the subject to temporarily hold treatment to a specified region or completely (i.e., due to an adverse event). This treatment modification and the reason for the temporary drug interruption should be documented in the subject's source documents. The lesions in the impacted area should continue to be counted in the lesion count during the period of treatment modification. See Section [6.8.2](#) for additional details.

6.8.2.2 Permanent Discontinuation of Treatment

The investigator may discontinue a subject's treatment if the subject/caregiver has failed to follow study procedures or to keep follow-up appointments. Appropriate documentation in the subject's study record and the study database regarding the reason for treatment discontinuation must be completed. See Section [6.8.2](#) for additional details.

Reasons for an investigator's withdrawal of a subject **from the treatment** may include, but are not limited to, the following:

- Safety (e.g., severe adverse reactions, pregnancy)
- When a concomitant medication or treatment likely to interfere with the results of the study is reported, or required, by the subject, the investigator will decide, in consultation with the CRO whether the subject is to be withdrawn.

Reason(s) for discontinuation from the treatment as listed in the study record will be entered into the study database as follows:

- Complete clearance confirmed by investigator prior to Week 12
- Adverse Event (including LSRs deemed to be significant by investigator)
- Withdrawal of Consent by Subject/Caregiver
- Lost to Follow-Up
- Other

6.8.3 Withdrawal from Study

A subject/caregiver may voluntarily withdraw from study participation at any time. If the subject/caregiver withdraws consent and discontinues from the study, the investigator will attempt to determine the reason for discontinuation and record the reason in the subject's study records and in the study database. In the event of discontinuation from the study prior to the

Week 12 visit, every effort should be made to have the subject return to the study site to complete the Week 12 evaluations (ET1 visit). If the subject/caregiver is unable or unwilling to return to clinic for the Week 12 visit, the investigator should discuss with the medical monitor the option to perform a remote Week 12 visit. All premature discontinuations and their causes must be carefully documented in the subject's study record and in the study database.

All Week 12 evaluations should be performed at the time of premature discontinuation as applicable if the subject discontinues prior to Week 12. If the subject discontinues after the Week 12 visit, the Week 24 evaluations should be performed. All data gathered on the subject prior to termination will be made available to the CRO. The investigative site should make all reasonable efforts to ensure the subject returns to complete the termination visit, even if the subject is not able to attend other study visits.

Study completion or reason(s) for discontinuation from the study as listed in the study record will be entered into the study database as follows:

- Withdrawal of Consent by Subject/Caregiver
- Lost to Follow-Up
- Adverse Event
- Other

Novan has the right to terminate or stop the study at any time. Should this be necessary, the investigator will ensure that proper study discontinuation procedures are completed.

6.8.4 Replacement of Subjects

Subjects who withdraw from the study will not be replaced.

6.8.5 Subjects Lost to Follow-up

All subjects who fail to return to the study site will be contacted by telephone to determine the reason(s) why the subject failed to return for the necessary visit or elected to discontinue from the study. If a subject/caregiver is unreachable by telephone after a minimum of three documented attempts (one attempt on three different days using at least 2 different forms of communication), a certified letter will be sent requesting that the subject contact the investigator to confirm the final status of their molluscum lesions and to return any outstanding study drug. These actions will be reported on the subject's study record and a copy of the follow-up letter maintained in the investigator's file. The certified letter should include the following questions:

- Please choose one of the following:
 - I/my child want to continue participating in this study.

- I/my child am no longer interested in participating in this study and withdraw my consent.
- At the time you chose to stop participating in study visits, was your/your child's molluscum contagiosum:
 - Resolved (no lesions left)
 - Resolving (number of lesions is decreasing)
 - Unchanged (number of lesions is similar to previous visit)
 - Worsening (number of lesions increased)

An investigator may withdraw a subject from the study when a subject is lost to follow-up.

6.9 Study Termination

Both Novan and the principal investigator reserve the right to terminate the study at the investigator's site at any time. Should this be necessary, Novan or a specified designee will inform the appropriate regulatory authorities of the termination of the study and the reasons for its termination, and the principal investigator will inform the IRB/IEC of the same. In terminating the study, Novan and the principal investigator will assure that adequate consideration is given to the protection of the subjects' interests.

7 DESCRIPTION OF STUDY ASSESSMENTS

The following study assessments will be done. Additional details can be found in in the Study Reference Manual and in the supportive online trainings.

7.1 Efficacy Assessments

7.1.1 Molluscum Contagiosum Lesion Counts

Molluscum contagiosum is a viral infection characterized by small, discrete, waxy, skin-colored, dome-shaped raised papules, an average of 3–5 mm in diameter. The papules may be umbilicated and contain a caseous plug. When the lesions are squeezed or traumatized, a creamy, grey-white material can be extruded. If the investigator cannot clearly differentiate the lesions as is the case for agminated (clustered) lesions this should be counted as one lesion. If the investigator can differentiate and count the umbilical tops separately, each lesion should be counted separately. The investigator should be consistent with the method of recording agminated lesions throughout the study.

For the purpose of this clinical trial, only treatable MC lesions are counted. Treatable lesions are any active (raised, palpable) MC lesions that are dome-shaped, pearly, and shiny white top centered papules that are at least 2 cm away from the ocular region. In clinic, investigators may choose to palpate the lesion to confirm if it is raised. Treatable region is any skin area containing a molluscum lesion, with the exception of the periocular region.

All study personnel who will perform lesion counts must pass the study training including lesion count training. Training on how to accurately count the number of MC lesions will be provided.

Mapping of lesions: At every visit from Baseline through Week 12, all lesions should be recorded on the body map and will clearly note the location of each lesion or agminated lesion. The lesion map is intended to assist study personnel in performing lesion counting and scar/keeloid assessment. The body map will also be shared with the subjects/caregivers at Week 2 to assist with counting of lesions.

Definition of Clearance: For the purpose of this study, “clear” means resolution of the active (raised, palpable) treatable molluscum lesion(s). After a lesion has cleared, the residual surface changes such as a pitted scar (indentation), hyperpigmentation, or hypopigmentation may remain. Additional details will be provided in the lesion count training. Complete clearance can only be confirmed by an in-clinic lesion count.

The same evaluator should perform lesion counts at Screening, Baseline, and Weeks 2, 4, 8 and 12/ET. In the event that this is not possible due to unforeseen circumstances, a different evaluator may evaluate the subject. All evaluators must pass the study training including lesion count training. It is particularly important to ensure the same evaluator performs the Baseline and Week 12/ET for lesion counts for a subject,

7.1.2 Other Assessments

7.1.2.1 BOTE Inflammation Score

Inflammatory reactions around MC lesions has been associated with imminent resolution of MC (sometimes referred to as “beginning-of-the-end” [“BOTE”] signs). Investigators should educate subjects and caregivers on the characteristic stages of BOTE as it is recognized as the natural course of self-limiting clearance of MC. BOTE may be associated with itching, but not pain. BOTE is usually asymptomatic, self-limited, localized to individual MC lesions, and does not require discontinuation of study treatment or additional treatment.

Investigators will assess the treatment area at each scheduled visit and use their medical judgement to differentiate between BOTE and LSRs. The BOTE Inflammation Score will be recorded at each visit ([Table 5](#)).

Table 5 BOTE Inflammation Score

Score	Global Assessment	Description
0	No inflammation	No evidence of local inflammation
1	Mild	Minimal erythema and/or edema
2	Moderate	Definite erythema and/or edema with or without hemorrhagic crusting
3	Severe	Erythema and edema with definite hemorrhagic crusting
4	Very Severe	Strong reaction spreading beyond the treated area, bullous reaction, erosions

7.1.2.2 Investigator Global Severity Assessment

The Investigator Global Severity Assessment will be completed by the investigator to assess overall impression of severity of MC and completed at Baseline, Week 12, and Week 24. The investigator will be asked to answer the following question:

Please choose the response below that best describes the overall molluscum severity of the subject.

0. None
1. Mild
2. Moderate
3. Severe
4. Very severe

7.1.2.3 Subject Global Severity Assessment

The Subject Global Severity Assessment will be completed by the subject/caregiver to assess overall impression of severity of MC and completed at Baseline, Week 12, and Week 24. The subject or caregiver will be asked to answer the following question:

Please choose the response below that best describes the severity of your/your child's molluscum contagiosum today.

0. None
1. Mild
2. Moderate
3. Severe
4. Very severe

7.1.2.4 Investigator Global Impression of Change

The Investigator Global Impression of Change will be completed by the investigator to assess their overall impression of change from baseline in overall MC condition at Weeks 12 and 24. The investigator will be asked to answer the following question:

Please choose the response below that best describes the overall change in the subject's molluscum contagiosum since he or she started taking the study medication.

1. Very much improved
2. Much improved
3. Minimally improved
4. No change
5. Minimally worse
6. Much worse
7. Very much worse

7.1.2.5 Subject Global Impression of Change

The Subject Global Impression of Change will be completed by the subject/caregiver to assess their overall impression of change from baseline in overall MC condition at Weeks 12 and 24. The subject or caregiver will be asked to answer the following question:

Please choose the response below that best describes the overall change in your/your child's molluscum contagiosum since you/your child started applying the study medication.

1. Very much improved
2. Much improved
3. Minimally improved
4. No change
5. Minimally worse
6. Much worse
7. Very much worse

7.1.2.6 Study Exit Interview

Study exit interviews may be conducted with a selected subset of subjects that complete Week 12. Consent will be obtained starting at Baseline, and the professional interview will be performed with the subject/caregiver after completion of Week 12. The objective of the interview is to better understand the subject/caregiver perspective of their MC and treatment experience.

7.2 Safety Assessments

7.2.1 Physical Exam

A brief physical examination will be performed to evaluate objective anatomic findings. This physical examination will be performed at Baseline and at Week 12/ET. At Baseline, the physical examination will include a directed examination of the skin condition prior to any

application of study drug. This skin assessment will include the presence or absence of individual features of erythema, flaking/scaling, crusting, swelling, vesiculation/pustulation, and erosion/ulceration. Any clinically significant changes in the physical exam from baseline will be recorded as AEs.

7.2.2 Pregnancy Testing

Urine pregnancy testing will be required for females 9 years of age and older unless they are post-menopausal or surgically sterile (see Section 9.4). UPTs will be collected at Screening (if in-clinic visit), Baseline, and Week 12/ET. In addition to having a negative UPT at Baseline, before the first application of study drug, females who are 9 years of age and older must be willing to use an acceptable form of birth control during the study. The following are considered acceptable methods of birth control for this study: hormonal contraceptives (combined estrogen and progestogen or progestogen only, including oral, injectable, transdermal or injectable formulations); intrauterine device (IUD); intrauterine hormone releasing system (IUS); bilateral tubal occlusion or ligation if performed ≥ 3 months prior to Baseline; same sex partner or partner who has had a vasectomy ≥ 3 months prior to Baseline; sexual abstinence with a documented acceptable method of birth control if the subject becomes sexually active; female or male condoms with or without spermicide; or a cervical cap, diaphragm, or sponge with spermicide. Women with tubal occlusion or ligations or whose partner had a vasectomy will be required to complete UPTs at the required timepoints if their procedure was done < 3 months prior to Baseline. Tubal ligations or occlusion procedures should be recorded as part of the subject's medical history if applicable.

7.2.3 Local Skin Reaction Assessment

The investigator (or designated evaluator) will assess localized skin reactions (LSRs) at Baseline (at least 30 minutes post-dose), and at any time during the visit at Weeks 2, 4, 8 and 12. The individual components of LSRs are scored separately on a scale of 0-4, with higher numbers indicating more severe reactions. The individual components include erythema, flaking/scaling, crusting, swelling, vesiculation/pustulation, and erosion/ulceration.

Compared to BOTE, LSRs are generally more diffuse, associated with significant itch or tenderness, may necessitate discontinuation of study treatment, and may need treatment for symptomatic relief (e.g. a topical corticosteroid or topical anesthetic). For very severe LSR, systemic corticosteroids may be considered.

Investigators will assess the treatment area at each scheduled visit and use their medical judgement to differentiate between BOTE and LSRs. When LSRs are clinically significant in the opinion of the investigator (i.e. they interfere with the subject's normal daily activities), s/he should report the condition as an AE(s) (e.g. application site erythema, application site edema).

Clinically significant LSRs that are reported as adverse events and/or subject reported intolerability (i.e. itching, pain) may result in an investigator directed temporary treatment hold

(drug holiday), and topical corticosteroids may be used to treat LSRs for up to 2 weeks. The subject may re-initiate study drug treatment prior to the next scheduled visit. Upon re-initiation (challenge) of study drug treatment, if a subject develops worsening LSRs (more severe than the first LSRs), allergic contact dermatitis may be suspected. In the event of suspected allergic contact dermatitis, photographs may be taken of the affected area(s) and transmitted to the CRO medical monitor for review and confirmation of allergic contact dermatitis prior to initiating patch testing. Consent must be in place for patch testing to occur. The investigator should also discuss the necessity of patch testing with the subject/caregiver. The investigator will then discontinue the subject from study drug treatment and treat the area(s) with corticosteroids for up to 2 weeks. If the subject provides consent/assent, the investigator will consult the CRO medical monitor to implement the process for patch testing. See Section 7.2.5 for information on patch testing.

Table 6 Local Skin Reaction Scale

	Erythema	Flaking/ Scaling	Crusting	Swelling	Vesiculation/ Pustulation	Erosion/ Ulceration
0	Not present	Not present	Not present	Not present	Not present	Not present
1	Slightly pink	Mild, limited	Isolated crusting	Minimal, limited	Fine vesicles	Superficial erosion
2	Pink or light red	Moderate	Crusting < 50%	Mild, palpable	Scant transudate or exudate	Moderate erosion
3	Red, restricted to treatment area	Coarse	Crusting > 50%	Moderate	Moderate transudate or exudate	Marked, extensive
4	Red extending outside treatment area	Scaling extending outside treatment area	Crusting extending outside treatment area	Marked swelling extending outside treatment area	Marked transudate or exudate	Black eschar or ulceration

7.2.4 Scarring/Keloid Assessment

Scar formation (scars/keloids/hypertrophic scars) will be assessed starting at the Week 4 visit through Week 12 and again at Week 24. Using the lesion map as a guide, the investigator will assess the treated areas for scar/keloid formation. All scars, including keloid/hypertrophic scars, that develop after the Baseline assessment should be captured as AEs and assessed for relatedness to study treatment.

7.2.5 Diagnosis of Allergic Contact Dermatitis and Patch Testing

After treatment is reintroduced post-LSR, if a subject experiences a stronger LSR (second LSR event) than the first LSR event, allergic contact dermatitis may be suspected. In order to confirm whether the reaction is allergic contact dermatitis, patch testing should be conducted. If the investigator determines that patch testing is appropriate, he/she should contact the CRO medical monitor to discuss next steps. Patch testing supplies will be provided once requested from the CRO medical monitor. Additional drug product for patch testing may be supplied through IWRS if the currently assigned subject's investigational product was assigned more than 60 days prior to the patch testing date(s) or if the subject had previously returned all their drug product.

Additionally, patch testing should be discussed with the subject/caregiver. If the subject/caregiver consents to patch testing and once the LSR has been completely resolved for a period of 2 weeks and up to 2 months, patch testing will commence. If allergic contact dermatitis is suspected, study drug should be permanently discontinued and an AE of allergic contact dermatitis should be recorded as the reason for discontinuation. Week 12/ET assessments should be completed at the time of discontinuation.

In the event of suspected allergic contact dermatitis developed, photographs may be taken of the affected area(s) and transmitted to the CRO medical monitor for review prior to initiating patch testing. See [Appendix 1](#) for further information.

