APPENDIX 1 PROCEDURE FOR SUSPECTED SENSITIZATION

After treatment is reintroduced post-LSR, if a subject experiences a stronger LSR (second LSR event) than the first LSR event, allergic contact dermatitis may be suspected. In order to confirm whether the reaction is allergic contact dermatitis, patch testing should be conducted. If the investigator determines that patch testing is appropriate and the patient/caregiver consent to patch testing, he/she should contact the CRO medical monitor to discuss. Once the LSR has been completely resolved for a period of 2 weeks and up to 2 months, patch testing may commence. Novan will provide more detailed patch testing instructions once requested from the CRO medical monitor. The site will use a study drug kit already assigned to the subject in order to complete the testing. Additional drug product for patch testing may be supplied through IWRS if the currently assigned subject's investigational product was assigned more than 60 days prior to the patch testing date(s) or if the subject had previously returned all their drug product.

For patch testing:

- Discontinue study treatment (see Section 7.2.3 regarding LSRs)
- Document the event as an AE and consult with the CRO medical monitor. Detailed instructions for the patch testing will be provided after discussion with the medical monitor.
- When applicable, challenge patch testing should be performed after all signs and symptoms of the LSR have been resolved for approximately 2 weeks to 2 months.
- The randomized study treatment will be applied to a naïve area on the participant's back or arm. Use the subject's most recently assigned study drug kit to obtain material for testing.
- The participant will return to the site approximately 48 hours after the application of the patches. Approximately 30 minutes, 24 hours and 48 hours after patch removal, the patch site(s) will be evaluated using the scale in Table 9. If the 48-hour reading is equivocal, it is recommended to evaluate the site at 72 to 96 hours after removal. Take photographs at every time point and transmit them to the medical monitor. Further instructions will be given after review of the photos.

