- At the last reading, the investigator will make the final interpretation of any challenge reactions. This last reading (at least 48 hours after patch removal) is critically important to distinguish irritant reactions (which fade) from true allergic reactions (which persist) and to identify allergic reactions that do not appear at the time of patch removal. See Table 10.

Table 9 Grading System for Patch Test Reactions (at each time point)

Score	Description
+/-	Doubtful reaction, faint macular erythema
+	Weak, non-vesicular reaction with erythema, infiltration, and papules
++	Strong vesicular reaction with erythema, infiltration, and papules
+++	Spreading bullous reaction
-	Negative reaction
IR	Irritant reaction

Table 10 Challenge Reaction Interpretation (based on the last reading (at least 48 hours after patch removal))

Score	Description
Negative	Might include an irritative reaction
Equivocal	Unable to determine
Positive*	Reaction definitely due to sensitization

*Judgement of “positive” reaction should be accompanied by ++ or greater reading at the last reading.

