### **13.6 Patch Testing**

A table summarizing any patch testing results by time point may be presented.

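### Allergic contact dermatitis is recorded as the AE on suspicion, before the confirming patch test, and no rule reconciles that term with the patch result

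*Protocol*

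**What the plan says.** Protocol 7.2.5 gives the patch test its purpose: "In order to confirm whether the reaction is allergic contact dermatitis, patch testing should be conducted". It also sets the timing: "once the LSR has been completely resolved for a period of 2 weeks and up to 2 months, patch testing will commence". Yet it acts before any test: "If allergic contact dermatitis is suspected, study drug should be permanently discontinued", and in the same sentence "an AE of allergic contact dermatitis should be recorded as the reason for discontinuation".

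Appendix 1 of the protocol is less specific about the record. It says "Document the event as an AE and consult with the CRO medical monitor" and names no AE term. On the result it says "At the last reading, the investigator will make the final interpretation of any challenge reactions", and Table 10 allows Negative, Equivocal or Positive.

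SAP 13.1 tabulates TEAEs, and TEAEs leading to study drug discontinuation, by MedDRA preferred term. On patch tests, SAP 13.6 says only "A table summarizing any patch testing results by time point may be presented".

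On stopping study drug, protocol 6.8.2, 7.2.5 and 8.7 tie it to suspicion. The synopsis and 7.2.3 first describe optional photographs, review and confirmation by the medical monitor, consent, and a discussion of patch testing. They then say "The investigator will then discontinue the subject from study drug treatment and treat the area(s) with corticosteroids for up to 2 weeks".

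**The concern.** The diagnostic term enters the database before the test that is meant to establish it, and nothing brings the result back to the term. Appendix 1 itself treats the last reading as what separates irritant reactions, which fade, from allergic ones, which persist. If the AE term is not revisited, that distinction never reaches the AE tables. Those tables would then count suspected ACD under the same term as confirmed ACD.

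Contact allergy is the one reaction for which this protocol has its own diagnostic appendix, so a reader of the safety section will look for its rate by arm. Appendix 1 leaves the term open where 7.2.5 prescribes it, so sites may also code the same situation differently.

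The order of steps before stopping study drug is a second, separate matter. A site reading 7.2.3 meets a different sequence from a site reading 8.7.

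**Working it through.** The plan states no figure on this point, so there is none to reproduce. The check is a comparison of passages, then an illustration of scale.

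**Passages in order of events**

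1. A stronger second local skin reaction (LSR) follows re-introduction of study drug, and ACD is suspected (6.8.2, 7.2.3, 7.2.5, 8.7, Appendix 1).
2. Study drug is permanently discontinued and the AE is recorded as ACD (7.2.5), or as an AE with no named term (Appendix 1).
3. The LSR resolves, and 2 weeks to 2 months pass.
4. The patch is worn for about 48 hours, and the last reading comes at least 48 hours after removal (Appendix 1).
5. The investigator gives the final Table 10 interpretation.
6. No later step exists. Protocol 9.2 and 9.3, Appendix 1, and SAP 13.1 and 13.6 contain no rule to keep, change or qualify the term. Table 8 lists a positive allergy test as evidence on causality, but no step brings the patch result back to the AE record.

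**Effect on the tables.** A reaction with onset on treatment that stops study drug falls both in Table 14.3.1.2.1 (TEAEs by preferred term) and in Table 14.3.1.6 (TEAEs leading to drug discontinuation), under whatever term step 2 supplied.

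**Timing against unblinding.** SAP Section 6 freezes and unblinds the database once all subjects have completed Week 12/ET1. The shortest path from resolution to last reading is 14 + 2 + 2 = 18 days. For a subject whose Week 12 visit (Day 85) is the last in the study, a reaction that resolves after about Day 85 − 18 = 67 cannot have a final reading by that visit. Any change of term for such a case could follow unblinding.

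**Scale (illustrative).** Inputs are protocol Tables 3 and 4 and the planned 425 per arm (10.2.1).

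- NI-MC302, SB206: 3 mild + 3 moderate = 6/237 = 2.5% (exact 95% CI 0.9% to 5.4%). Vehicle: 0/117.
- NI-MC301, SB206: the term is absent from a table of events at 2% or more in either arm. Since 5/235 = 2.1% would be listed and 4/235 = 1.7% would not, the count is at most 4/235.
- Pooled SB206: 6/472 = 1.3% to (6 + 4)/472 = 2.1%.
- Per 425: 425 × 6/472 = 5.4 to 425 × 10/472 = 9.0. At the NI-MC302 rate alone, 425 × 6/237 = 10.8.

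The documents give no share of suspected cases that prove negative, equivocal or untested. If that share is assumed to be 25% to 75%, the affected records number 0.25 × 5.4 = 1.4 to 0.75 × 9.0 = 6.8 on the pooled range, and 2.7 to 8.1 at the NI-MC302 rate.

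**Stopping and confirmation, side by side**

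| Place | When study drug stops | What confirms ACD |
|---|---|---|
| Synopsis, 7.2.3 | after the photo review and discussion are described | medical monitor, from photographs |
| 6.8.2 | when a more severe second LSR occurs | patch testing recommended; nothing said to confirm |
| 7.2.5 | on suspicion, permanently | patch test; the monitor only reviews |
| 8.7 | on suspicion | not stated |

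**The case against.** The strongest reply is that the plan already exposes the case-level facts. SAP Section 6 calls for a listing of subjects requiring a narrative, which includes those with an LSR suggestive of ACD. Listing 16.2.9.5 shows patch results, Table 14.3.6.5 is in the planned index, and the DSMB sees completed patch results. With about a dozen cases or fewer, a careful reader could separate suspected from confirmed ones. Treatment-related AEs remain under follow-up for up to a year, and monitors resolve data queries, so a site could amend the term. The table shells are in a separate file, and the last reading is itself a time point, so SAP 13.6 may be intended to cover the final interpretation. All of this stands. It means confirmed cases are not hidden. It does not supply a rule for the term, correct the AE tables, or turn an optional table into a committed one.

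A reader might infer that patch-negative cases will be reported as sensitization. The documents do not say so. No passage requires the term to stay after a negative test, and in Table 10 the word sensitization belongs to a Positive result only.

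A reader might also infer a flat contradiction on stopping study drug. That is too strong. The synopsis and 7.2.3 also start from suspected ACD, the photographs are optional, every section stops study drug before patch testing, and 6.8.1 lets the investigator stop treatment at any time if medically necessary. What remains is an ambiguity of sequence and a difference over what confirms ACD.

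Nor do the data show that nearly all such cases would be on SB206. Six against none under roughly 2:1 allocation would arise with equal rates about (237/354)^6 = 9% of the time.

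**Conclusion.** The point holds as a gap in reconciliation. ACD is entered as the AE on suspicion, the confirming test comes later, and nothing in either document links the two. Negative, equivocal and untested cases can therefore remain as ACD in two sets of safety tables.

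The number of records is likely to be small: about 5 to 9 suspected cases among 425 SB206 subjects, or about 11 at the NI-MC302 rate alone, of which an unknown share would be unconfirmed. This rests on three assumptions: that suspected ACD codes to the preferred term used in the earlier studies, that those earlier cases resemble the ones this procedure will generate, and that the rates carry over. An untested case is unconfirmed, which is not the same as non-allergic.

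No efficacy endpoint is touched, and no inferential safety analysis is planned. The change is still worth making, because it costs little and settles how ACD will be reported before unblinding.

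**What to change.** - **Protocol 7.2.5 and Appendix 1:** record the event at suspicion as the observed reaction, with a suspected-ACD flag. Update the AE term after the final Table 10 interpretation. Keep untested cases as suspected, not tested. Document any change of term made after the Week 12 unblinding.
- **SAP 13.6:** make the table mandatory. Tabulate suspected, tested, positive, equivocal, negative and not tested by arm, with the Safety Population as denominator.
- **Protocol synopsis, 6.8.2, 7.2.3, 7.2.5 and 8.7:** reconcile the passages on when study drug is stopped relative to photo review, and on what counts as confirmation of ACD. No clinical rule is proposed here.

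The cost is wording in both documents, one small table mostly from data already planned (plus the flag), and a follow-up query on roughly a dozen AE records or fewer.
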